1.4.1. Clinical Experience from the Treatment of Strongyloidiasis

In 4 clinical studies¹⁹ involving a total of 109 patients given either one or two doses of 170 to 200 μ g/kg of ivermectin, the following AEs were reported as possibly, probably, or definitely related to ivermectin:

Body as a Whole: asthenia/fatigue (0.9%), abdominal pain (0.9%)

Gastrointestinal: anorexia (0.9%), constipation (0.9%), diarrhoea (1.8%), nausea (1.8%), vomiting (0.9%)

Nervous System/Psychiatric: dizziness (2.8%), somnolence (0.9%), vertigo (0.9%), tremor (0.9%)

Skin: pruritus (2.8%), rash (0.9%), and urticaria (0.9%).

The following laboratory abnormalities were seen regardless of drug relationship:

Elevation in alanine aminotransferase (ALT) and/or aspartate aminotransferase AST (2%), decrease in leukocyte count (3%). Leukopenia and anaemia were seen in one patient.

In comparative trials, patients treated with ivermectin experienced more abdominal distention and chest discomfort than patients treated with albendazole. However, ivermectin was better tolerated than thiabendazole in comparative studies involving 37 patients treated with thiabendazole.

1.4.2. Clinical Experience from the Treatment of Onchocerciasis

In clinical trials¹⁹ involving 963 adult patients treated with 100 to 200 μ g /kg ivermectin, worsening of the following Mazzotti reactions during the first 4 days post-treatment were reported: arthralgia/synovitis (9.3%), axillary lymph node enlargement and tenderness (11.0% and 4.4%, respectively), cervical lymph node enlargement and tenderness (5.3% and 1.2%, respectively), inguinal lymph node enlargement and tenderness (12.6% and 13.9%, respectively), other lymph node enlargement and tenderness (3.0% and 1.9%, respectively), pruritus (27.5%), skin involvement including oedema, papular and pustular or frank urticarial rash (22.7%), and fever (22.6%).

Ophthalmological conditions were examined before treatment, at Day 3, and months 3 and 6 after treatment with 100 to 200 μ g /kg ivermectin. Changes observed were primarily deterioration from baseline 3 days post-treatment. Most changes either returned to baseline condition or improved over baseline severity at the month 3 and 6 visits. The percentages of patients with worsening of the following conditions at Day 3, month 3 and 6, respectively, were: limbitis: 5.5%, 4.8%, and 3.5% and punctate opacity: 1.8%, 1.8%, and 1.4%. The corresponding percentages for patients treated with placebo were: limbitis: 6.2%, 9.9%, and 9.4% and punctate opacity: 2.0%, 6.4%, and 7.2%.

The following clinical adverse reactions were reported as possibly, probably, or definitely related to the drug in $\geq 1\%$ of the patients: facial oedema (1.2%), peripheral oedema (3.2%), orthostatic hypotension (1.1%), and tachycardia (3.5%). Drug-related headache and myalgia occurred in $< 1\%$ of patients (0.2% and 0.4%, respectively). However, these were the most common adverse experiences reported overall during these trials regardless of causality (22.3% and 19.7%, respectively).

A similar safety profile was observed in an open study in paediatric patients ages 6 to 13.

The following ophthalmological side effects do occur due to the disease itself but have also been reported after treatment with ivermectin: abnormal sensation in the eyes, eyelid oedema, anterior uveitis, conjunctivitis, limbitis, keratitis, and chorioretinitis or choroiditis. These have rarely been severe or associated with loss of vision and have generally resolved without corticosteroid treatment.

The following laboratory adverse experiences were reported as possibly, probably, or definitely related to the drug in $\geq 1\%$ of the patients: eosinophilia (3%) and haemoglobin increase (1%).

1.4.3. Post-Marketing Experience

Hypotension (mainly orthostatic hypotension), worsening of bronchial asthma, toxic epidermal necrolysis, Stevens-Johnson syndrome, seizures, hepatitis, elevation of liver enzymes, and elevation of bilirubin have been reported.¹⁹ Conjunctival haemorrhage has been reported in the treatment of Onchocerciasis.

Further details regarding the clinical data can be found in the IB or the Summary of Product Characteristics.¹⁹

1.5. Risk/Benefit Assessment

Further information about the known and expected benefits and risks and reasonably expected AEs of ivermectin may be found in the current IB and the Summary of Product Characteristics.¹⁹

Details of these risks and the proposed strategy to mitigate/monitor these risks are detailed in [Table 1](#).

In this study, safety will be monitored closely both by subjective reporting and by objective means i.e., serial assessments of vital signs, clinical laboratory evaluations data, physical examinations, 12-lead electrocardiogram (ECG) and comprehensive neurological examinations. This study will be run in a Clinical Research Unit (CRU) with immediate access to hospital facilities for the treatment of medical emergencies. Subjects will remain monitored in the clinic for the first 7 days of dosing and will only be discharged from the CRU at the end of Day 7 if the Investigator deems it safe to do so.

Table 1: Risk/Benefit Assessment

Potential Risk of Clinical Significance	Summary of Data/Rationale for Risk	Mitigation Strategy
Skin rashes and pruritus	SmPC	Physical examinations will be performed regularly throughout the study to identify any rashes and overall TEAEs will be monitored.
Cardiovascular changes	SmPC	Heart rate and blood pressure will be frequently monitored during the study by supine and standing vital signs.
CNS changes	SmPC	Comprehensive neurological examinations will occur frequently during the study to identify any changes.
Gastrointestinal system effects	SmPC	Clinical monitoring of body weight and standard safety laboratory parameters, as well as overall TEAEs will be monitored. Subjects will be withdrawn if effects are severe.
Respiratory system changes; exacerbation of asthma	SmPC	Asthmatic subjects will be excluded.
Ophthalmologic changes	SmPC; IB	Comprehensive neurological examinations will occur frequently during the study to identify any changes.
Haematological changes	SmPC	Subjects will be closely monitored with frequent blood tests during the study. Haematology parameters will be closely monitored throughout the course of the study as dose escalation proceeds. Escalation to higher doses and exposures will only occur if emerging data indicates this is safe and appropriate. Stopping criteria have been added for clinically significant lab results. If indicated, no further dose escalation will occur.
Liver dysfunction: elevation in ALT, AST and/or bilirubin; acute hepatitis.	SmPC	Subjects will be closely monitored with frequent blood tests during the study. Liver function test parameters must be entirely normal for study eligibility and no alcohol will be allowed from 48 hours prior to Day -1. Clinical chemistry parameters will be closely monitored throughout the course of the study as dose escalation proceeds. Escalation to higher doses and exposures will only occur if emerging data indicates this is safe and appropriate. Stopping criteria have

		been added for clinically significant lab results. If indicated, no further dose escalation will occur.
Drug-drug interaction	In pre-clinical studies, ivermectin has been shown to be most likely hepatically metabolised through the CYP3A4 system. In pre-clinical studies, a subpopulation of CF-1 mice with P-gp deficiency presented with a 10 to 100-fold increase in ivermectin sensitivity and increased concentration of ivermectin were found in the intestine and in the brain.	Concomitant medication restrictions; co-administration of ivermectin and drugs known to be CYP3A4 or P-gp substrates will be avoided.
Risk of local or systemic allergic response.	SmPC and risk from multiple dose accumulation	This study will be performed in a CRU equipped to deal with allergic responses and anaphylaxis with access to hospital emergency facilities, if needed. Sentinel subjects will be dosed in each cohort. During outpatient periods there will be close contact with the CRU to ensure any type of local or systemic reaction is highlighted.
Exposure to SARS-CoV-2	Exposure to other infections is always a risk when study subjects attend a clinical research facility, but increased risk due to SARS-CoV-2 pandemic.	A SARS-CoV-2 test (according to the current UK standard testing) screen will be performed at Screening and prior to any inpatient stays. Additional SARS-CoV-2 tests will be carried out, as required, if any subject displays any of the signs and symptoms. The subject's temperature will be taken at the start of every visit to help assess SARS-CoV-2 status. In addition to temperature checks, subjects will be asked SARS-CoV-2 standard questions prior to all visits to the CRU. The CRU has been in operation throughout the lockdown period and will continue to monitor the situation and adhere to current UK Government advice around social distancing and personal protective equipment to protect site staff and study subjects. The requirement for, and duration of, inpatient stays has been minimised where safely possible. Distancing is in place within the CRU to ensure the least amount of contact possible, with both staff and subjects wearing face coverings. Any communal areas have been put out

		of use with restrictions on use of bathrooms and showers to ensure safety.
--	--	--

Abbreviations: ALT – alanine aminotransferase; AST – aspartate aminotransferase; CNS – Central Nervous System; CRU – Clinical Research Unit; CYP – cytochrome P450; IB – Investigator Brochure; P-gp – P-glycoprotein; SARS-CoV-2 – severe acute respiratory syndrome coronavirus-2; SmPC – summary of product characteristics; TEAE – treatment emergent adverse event.

2. OBJECTIVES AND ENDPOINTS

2.1. Objectives

2.1.1. Primary Objective

The primary objective of this study is to characterise the PK profile of ivermectin following daily repeated doses for 28 days.

2.1.2. Secondary Objectives(s)

The secondary objective of this study is to characterise the safety and tolerability profile of daily repeated dosing of ivermectin for 28 days.

2.1.3. Exploratory Objective

The exploratory objective of this study is to evaluate the potential of ivermectin as a prophylactic measure to SARS-CoV-2 infection.

2.2. Endpoints

2.2.1. Primary Endpoint

The primary endpoints of the study are plasma PK concentrations including but not limited to: maximum plasma concentration (C_{max}), time to reach C_{max} (t_{max}), [REDACTED] area under the plasma concentration-time curve from zero to 24 hours (AUC_{0-24h}), [REDACTED] apparent terminal half-life ($t_{1/2}$).

2.2.2. Secondary Endpoint(s)

The secondary endpoint of the study is the clinical safety data from AE reporting, 12-lead ECG, vital signs, clinical laboratory evaluations, and physical and neurological examinations in healthy male subjects.

2.2.3. Exploratory Endpoints

The exploratory endpoint of the study is the occurrence of SARS-CoV-2 infection as confirmed by reverse transcription polymerase chain reaction (RT-PCR) test and/or serology.

3. STUDY DESIGN

This is a Phase I, double-blind, placebo-controlled, randomised study to determine the PK profile, safety and tolerability of multiple oral doses of ivermectin in healthy male subjects

Up to 24 subjects are planned to be enrolled into 3 cohorts comprising 8 subjects each. In each cohort, 6 subjects will be randomised to receive ivermectin and 2 subjects will be randomised to receive placebo. Multiple-dose oral administration of once daily ivermectin or placebo will occur for 28 days. All cohorts will consist of 2 sentinel subjects, of whom 1 subject will receive ivermectin and 1 subject will receive matched placebo. The remaining subjects in each cohort (6 subjects; 5 subjects ivermectin and 1 subject placebo) will commence treatment after satisfactory review of the safety data up to a minimum of 4 hours post-dose on Day 7 from the sentinel subjects, if deemed safe to do so by the Principal Investigator.

The planned dose levels are presented in [Table 2](#).

Table 2: Planned Dose Levels

Cohort 1	Loading dose of 200 µg/kg on Day 1, then 50 µg/kg/day from Day 2 to Day 28
Cohort 2	Loading dose of 200 µg/kg on Day 1, then 75 µg/kg/day from Day 2 to Day 28
Cohort 3	Loading dose of 200 µg/kg on Day 1, then 100 µg/kg/day from Day 2 to Day 28

The dose levels will be administered in an ascending order; progression to the next dose level, and dose selection, will be based on the safety, tolerability and available PK data from the preceding dose cohort(s) (safety, tolerability and PK data [up to Day 14] from a minimum of

4 ivermectin and 1 placebo subjects in the preceding dose cohort). Except for the starting dose, the doses outlined in the protocol are preliminary, with actual subsequent doses determined based on an ongoing evaluation of the safety, tolerability, and PK data by the Safety Review Committee (SRC; described in [Section 3.2.1](#)).

Subjects will be required to attend the CRU for a Screening visit within 28 days prior to first dosing to ensure they meet the inclusion/exclusion criteria and are in good health. Subjects will be admitted to the CRU 1 day prior to first dosing (Day -1) for collection of baseline safety assessments and will receive their first dose of ivermectin or placebo in the morning of Day 1, following an overnight fast. Subsequent daily doses of ivermectin or placebo will be administered in the morning in the CRU from Day 2 to Day 7, following an overnight fast. Subjects will reside in the CRU until at least 4 hours post-dose on Day 7 for the collection of safety assessments and PK blood samples but may reside for longer if deemed necessary by the Investigator. From Day 8 to Day 27, subjects will self-administer their daily dose of ivermectin or placebo at home following an overnight fast, with the exception of outpatient visits on Day 14 and Day 21 which will be administered in the CRU. Subjects will be readmitted to the CRU on Day 28 to receive their final dose of ivermectin or placebo and will be discharged on Day 29 following safety assessments and PK blood samples. Subjects will return to the CRU for outpatient visits on Days 32, 35 and 42 for safety assessments and PK blood samples.

A detailed plan of study assessments is provided in [Appendix 1](#).

3.1. Rationale for Study Design

This study is designed to evaluate the PK profile, safety and tolerability of multiple (28-day) ascending doses of ivermectin in healthy male subjects. This information will help to establish the dose and regimen suitable for administration in future studies.

In line with the European Medicines Agency Guideline on strategies to identify and mitigate risks for first-in-human and early clinical trials with Investigational Medicinal Products (IMPs)²⁰, all cohorts will consist of 2 sentinel subjects; 1 receiving ivermectin and 1 receiving placebo. The remaining 6 subjects in each cohort (5 receiving ivermectin and 1 receiving placebo) will be dosed only if safe to do so based on the safety data from up to a minimum of 4 hours post-dose on Day 7 from the sentinel subjects.

To mitigate risk to subjects in this study, the cohorts will be recruited sequentially with progression through the cohorts dependent on adequate safety and PK data from the previous cohort and approval by the SRC. The SRC findings at each review will be documented.

To ensure compliance with the dosing regimen whilst outside the CRU, subjects will be contacted regularly by phone or text message to ensure that the correct number of tablets are being taken, and that doses have been following an overnight fast.

Since the safety profile in humans over 28 days of consecutive dosing has not yet been investigated, all subjects will be closely monitored. Standard assessments to evaluate safety and tolerability, including vital signs, physical examinations, neurological examination, 12-lead ECGs, clinical laboratory evaluations and AE collection will be utilised in this study.

3.2. Dose Rationale

Ivermectin has been used in clinical practice for over 30 years, since 1987 with an estimated 1.3 billion treatments for river blindness.¹⁴ The standard approved dose of 200 µg/kg is taken once to three times a year¹⁴ but much higher doses, up to 2,000 µg/kg taken in split doses over

one week found ivermectin to be generally well tolerated, with no difference in AEs between placebo and these highest doses.¹⁶ However, despite these high doses no study has investigated continuous daily dosing for one month which would have the potential for a prophylaxis treatment of COVID-19.

In healthy volunteers receiving oral doses of ivermectin up to 120 mg (equivalent to a dose per body weight of 1404 to 2000 µg/kg), the C_{max} was 247.8. ± 158.9 ng/ml with no significant increase in AEs recorded compared to the placebo treated group.¹⁶ This value is equivalent to approximately 2.2 times the minimum mean C_{max} after 13 weeks of repeated daily oral treatment at the lowest NOAEL in rats and is similar to the lowest mean C_{max} after 13 weeks of repeated daily oral treatment at the NOAEL in dogs [Table 3](#).

After 3 repeated administrations of 30 mg ivermectin three times in a week (equivalent to 347 to 594 µg/kg every fourth day or 149 to 232 µg/kg/day) in healthy volunteers, the mean C_{max} and $AUC_{0-\infty}$ were 87.0 ng/ml and 2819.4 ng.h/mL, respectively.¹⁶ When compared to the animal data after 13 weeks daily oral treatments with ivermectin at the NOAELs, these values are 1.2 to 6.4 lower than the mean C_{max} values found in rats and dogs, and 2 times higher to 2 times lower than the mean AUC_{0-24h} values found in rats and dogs, respectively dogs [Table 3](#).

Table 3: Summary of the Main Toxicokinetic Parameters from Selected Preclinical Studies and the corresponding HED at the NOAELs¹²

Study Type	Species	NOAEL	HED at the NOAEL	C_{max} at the NOAEL (ng/ml)		AUC_{0-24h} at the NOAEL (ng h/ml)		Dose Effect	Accumulation
				Males	Females	Males	Females		
13-weeks DRF study in rats	Wistar rats	1	161 µg/kg/day	Day 1: 81.6 Day 91: 128	Day 1: 91.5 Day 91: 112	Day 1: 1417 Day 91: 1629	Day 1: 1337 Day 91: 1431	More than dose proportional increase	Slight accumulation (dose ≥ 1mg/kg/day)
13-week oral toxicity study in rats	Wistar rats	3	484 µg/kg/day	Day 1: 417 Day 88: 558	Day 1: 367 Day 88: 508	Day 1: 4770 Day 88: 7786	Day 1: 4803 Day 88: 7470	More than dose proportional increase in the 1-3 mg/kg/day range	Slight accumulation
13-week oral toxicity study in dogs	Beagle dogs	0.5	278 µg/kg/day	Day 1: 195 Day 90: 365	Day 1: 209 Day 90: 282	Day 1: 2282 Day 90: 5629	Day 1: 2494 Day 90: 4166	Dose proportional increase in exposure at doses below the NOAEL	Accumulation

Abbreviations: AUC_{0-24h} – area under the plasma concentration-time curve from zero to 24 hours; C_{max} – maximum plasma concentration; DRF – dose range finding; HED – human equivalent dose; NOAEL – no observed-adverse-effect level.

In cases of severe crusted scabies, the Centers for Disease Control and Prevention (CDC) recommends a dosing regimen of 200 µg/kg up to 7 times for a 28-day period (dosing on Day 1, Day 2, Day 8, Day 9, Day 15, Day 22 and Day 28).²¹ This gives a total dose per month of 1400 µg/kg. These recommendations are also endorsed by the European Academy of Dermatology and Venerology²² as well as the Department of Health and Families of the Northern Territory Government of Australia.²³

The proposed dosing regimen is over a 28-day period consisting of a first loading dose of 200 µg/kg for the first day followed by once daily dosing of either 50, 75 or 100 µg/kg/day for

27 days. The loading dose of 200 µg/kg in all cohorts is within the approved dose range of the summary of product characteristics¹⁹ with the first cohort then having continuous daily dosing of 50 µg/kg/day for 27 days, the equivalent of a 200 µg/kg loading dose plus cumulative continuous daily dose of 1350 µg/kg (which is less than the CDC crusted scabies dose over a month, 1400 µg/kg) and combined dose would be less than 2000 µg/kg taken in split doses over one week.

The study has been designed to ensure the safety of the subjects by careful monitoring of individual subjects and review of safety data before dose escalation. The study design has the following features:

- Sentinel dosing for each cohort
- Safety data review before dose escalation
- Careful monitoring of the subjects with a one-week inpatient stay followed by once weekly on-site visits during the dosing phase and a final visit 2 weeks after the last dose.

In conclusion, for the proposed dosing regimen over 28-day period consisting of a first loading dose of 200 µg/kg followed by once daily dosing of either 50, 75 or 100 µg/kg/day for 27 days, in healthy volunteers, is expected to be well tolerated due to:

- Substantial exposure to Ivermectin since 1987
- Shorter duration of the study (4 weeks in humans vs 13 weeks in rats/dogs)
- Known safety profile of ivermectin at doses much higher than the approved dosages (up to 2000 µg/kg was tested in healthy volunteers with no significant increase in adverse events recorded compared to placebo) and the one-month treatment regimen for crusted scabies
- Study design, allowing for close monitoring of subjects and careful dose escalations after SRC reviews.

3.2.1. Safety Review Committee

Decisions for dose escalation between dose cohorts will be taken during an SRC meeting. The objectives of the SRC meetings are to review data from the current and previous cohort(s) and define the dose to be tested in the next cohort.

The SRC will comprise at a minimum:

- The Principal Investigator
- The Sponsor Medical Monitor
- MAC Project Manager for purpose of recording meeting minutes

Safety Review Committee meetings will be scheduled to occur once quality-controlled safety, tolerability and plasma PK data up to at least Day 14 are available from a minimum of 4 active and 1 placebo subjects. For the Cohort 2 data SRC meeting onwards, available safety, tolerability and plasma PK data up to Day 28 from previous cohorts will be reviewed.

The safety and tolerability data to be reviewed will include, at a minimum, AEs, physical examinations, comprehensive neurological examinations, 12-lead ECGs, vital signs and clinical laboratory evaluation results, summarised by the Investigator in an Interim Safety Report.

Further details on the operation of the SRC will be defined in a standalone supporting document. Details regarding the safety stopping criteria are provided in [Section 3.2.2](#).

3.2.2. Dose Escalation and Adjustment Criteria

3.2.2.1. Criteria for Stopping Dose Escalation

- PK Stopping Criteria: based on review of the accumulation ratio (RA). Dose escalation will not proceed if this is deemed to pose a clinically significant risk to subjects by the SRC members.
- Safety Stopping Criteria: Dose escalation will not proceed if any of the following occur in ivermectin-treated subjects:
 - One or more Hy's Law cases in subjects who have been administered ivermectin. Hy's Law is defined as AST or ALT ≥ 3 x upper limit of normal (ULN) and bilirubin ≥ 2 x ULN, in the absence of a significant increase in alkaline phosphatase (ALP) and in the absence of an alternative diagnosis that could explain the increase in bilirubin.
 - A 'serious' adverse reaction (see [Section 7.6.1.2](#) for definition of 'serious') in 1 subject, i.e., a serious adverse event (SAE) that is considered at least possibly related to ivermectin administration.
 - 'Severe' non-serious adverse reaction, i.e., a severe non-serious AE considered as at least possibly related to ivermectin administration, in 2 subjects in the same cohort, independent of within, or not within, the same system-organ class (SOC).
 - Clinically significant abnormalities in laboratory parameters in 2 or more subjects within the same cohort indicating dose-related intolerance, considered related to ivermectin.
 - Other findings that indicate dose escalation should be halted, e.g., if there is an unacceptable tolerability profile based on the nature, frequency and intensity of observed AEs and/or clinical safety monitoring.

If any of these stopping criteria are met, the SRC should stop further dose escalation. The SRC will determine whether the dose level should be repeated, whether a lower dose should be tested, or whether the study should be terminated. Progression to subsequent cohorts (which may include lower doses) may be approved by the SRC subject to satisfactory review of the available PK, safety and tolerability data. Alternatively, the SRC may conclude it is inappropriate to continue to another cohort, in which case the study will be terminated. If significant safety concerns arise during dosing of a cohort, the SRC will review all available data and, considering the criteria above, decide whether it is appropriate to continue.

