1.4. Clinical Experience

Ivermectin is a potent anthelmintic drug with a good and well described safety profile. Ivermectin has been used in clinical practice for over 30 years, since 1987 with an estimated 1.3 billion treatments for river blindness.¹⁴ This good safety profile may be attributed to its high affinity to invertebrate neuronal glutamate-coupled chloride channels and its inability to cross the blood–brain barrier in humans and other mammals.¹⁵ In addition, ivermectin has been administered to healthy patients at doses 7 to 10 times the maximum approved therapeutic dose, with no severe adverse events (AEs) being reported.^{16,17}

Tolerance to the compound has been assessed in healthy volunteers and in patients; adverse effects are usually mild and transient. but their severity may be increased in patients infected with more than one parasite, particularly in the case of infestation with *Loa loa*.

Following oral administration of ivermectin to healthy volunteers, plasma concentrations are relatively proportional to the dose level in the 30 to 120 mg dose range (i.e., 333-2000 µg/kg).¹⁶

The mean peak plasma concentration of the major component (H2B1a), observed approximately 4 hours after oral administration of a single 12 mg dose of ivermectin in tablet form is 46.6 (\pm 21.9) ng/mL. Ivermectin plasma concentration increases with increasing doses in a generally proportional manner. Ivermectin is absorbed and metabolised in the human body and ivermectin and/or its metabolites are excreted almost exclusively in faeces, whilst less than 1% of the administered dose is excreted in urine.¹⁸ The plasma half-life of ivermectin is about 12 hours (range in human healthy volunteers: 11.1 to 36.6 hours) and that of the metabolites is about 3 days.

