11.5.2.1. Derivation of Pharmacokinetic Parameters

Pharmacokinetic parameters will be derived from individual plasma concentration data of ivermectin by noncompartmental analysis. The PK parameters derived to assess the multiple dose PK of ivermectin are shown in Table 6.

Table 6: Pharmacokinetic Parameters

Abbreviation	Definition
C_{max}	Maximum plasma concentration
t_{max}	Time of maximum plasma concentration
AUC_{0-24h}	Area under the plasma concentration-time curve from zero to 24 hours
$t_{1/2}$	Apparent terminal half-life
RA	Accumulation ratio

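### Does the accumulation ratio (RA) in the PK stopping criterion need a definition in the protocol, given that Day 1 is a larger loading dose?

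*Protocol*

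**What the plan says.** Section 3.2.2.1 of the protocol opens its list of grounds for halting escalation with "PK Stopping Criteria: based on review of the accumulation ratio (RA"). It sets no numerical limit. Escalation stops if the SRC members judge that the ratio poses a clinically significant risk.

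Elsewhere RA is only a label. Section 11.5.2.1 says "The PK parameters derived to assess the multiple dose PK of ivermectin are shown in Table 6", and Table 6 expands RA to accumulation ratio without further detail. Section 11.5.2.2 describes how AUC0-24h, Cmax and half-life are obtained and does not mention RA. Section 11.5.2 sends the full PK analysis to a PK Analysis Plan. SAP Section 1.1 puts PK outside its scope, and SAP Section 4.7 leaves SRC analyses to the SRC charter.

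On dosing, Section 3.2 states "The proposed dosing regimen is over a 28-day period consisting of a first loading dose of 200" µg/kg, followed by 50, 75 or 100 µg/kg/day. Section 3 confirms that there is no gap: "Subsequent daily doses of ivermectin or placebo will be administered in the morning in the CRU from Day 2 to Day 7".

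The only accumulation data shown are the animal data in Table 3, at one constant dose per study. For AUC0-24h, male rats at 1 mg/kg have "Day 1: 1417 Day 91: 1629" and male dogs have "Day 1: 2282 Day 90: 5629".

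**The concern.** An accumulation ratio normally divides exposure on a late day by exposure on Day 1 at the same dose, as the Table 3 data allow. Here no subject has a drug-free starting profile at the maintenance dose. Day 1 is at a higher dose, and Day 2 carries over drug from Day 1. The usual meaning of RA therefore cannot be taken for granted.

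If someone divided Day 14 or Day 28 exposure by Day 1 exposure without adjustment, the result would be too small, and it would double from Cohort 1 to Cohort 3 through dose arithmetic alone. Dose-normalising removes that but assumes proportional exposure between 200 µg/kg and the daily dose. The quantified human statement, "plasma concentrations are relatively proportional to the dose level in the 30 to 120 mg dose range", covers doses above the 3 to 21 mg in Table 4. A ratio derived from the terminal half-life avoids the two-dose comparison, but the washout samples come after Day 28, while a cohort's escalation review may use data to Day 14. At stake would be an SRC reading reassurance or alarm from a number whose basis it did not know.

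**Working it through.** **Inputs.** Doses are from Table 2 and tablet counts from Table 4. On half-life, Section 1.4 says "The plasma half-life of ivermectin is about 12 hours (range in human healthy volunteers: 11.1 to 36.6 hours"). A time to peak of 4 h is also from Section 1.4. One-compartment oral kinetics and proportional exposure are assumptions made here.

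**The plan's own figure.** Section 3.2 gives 1350 µg/kg for the Cohort 1 daily doses after the loading dose: 27 × 50 = 1350. It reproduces.

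**Dose factor.** 200/50 = 4.00, 200/75 = 2.67, 200/100 = 2.00.

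**Same-dose accumulation.** With C(t) = D·ka/(ka − ke)·(e^(−ke·t) − e^(−ka·t)), ke = ln 2/half-life, and ka solved from ln(ka/ke)/(ka − ke) = 4 h:

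- First-dose AUC0-24h per unit dose = ka/(ka − ke)·[(1 − e^(−24ke))/ke − (1 − e^(−24ka))/ka].
- Steady-state AUC over 24 h per unit dose = 1/ke.
- Half-life 12 h: ke = 0.0578, ka = 0.671, ratio 17.31/12.58 = 1.38.
- Half-life 36.6 h: ke = 0.0189, ka = 1.014, ratio 52.80/18.65 = 2.83.

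The raw Day 28/Day 1 ratio is this value times (daily dose/200):

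| Half-life | Dose-normalised | Raw, Cohort 1 | Raw, Cohort 2 | Raw, Cohort 3 |
|---|---|---|---|---|
| 12 h | 1.38 | 0.34 | 0.52 | 0.69 |
| 36.6 h | 2.83 | 0.71 | 1.06 | 1.42 |

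Full superposition of all 28 doses gives the same values, and Day 14 agrees with Day 28 within 0.01. With time to peak from 2 to 6 h, the normalised ratio is 1.35 to 1.42 at 12 h and 2.78 to 2.90 at 36.6 h.

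**Table 3, same-dose AUC ratios (males, females).** Rat 1 mg/kg: 1629/1417 = 1.15, 1431/1337 = 1.07. Rat 3 mg/kg: 7786/4770 = 1.63, 7470/4803 = 1.56. Dog: 5629/2282 = 2.47, 4166/2494 = 1.67.

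**Sensitivity to proportionality.** If exposure varies as dose^b, the normalised ratio is multiplied by (daily dose/200)^(b − 1). For an assumed b of 0.8 this is 1.32, 1.22 and 1.15 in Cohorts 1, 2 and 3. For b of 1.2 it is 0.76, 0.82 and 0.87.

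**Alternating tablets.** In all of Cohort 2 and two weight bands of Cohort 3 the daily count alternates. With no missed dose, Days 14 and 28 fall on the lower count and Day 21 on the higher. In Cohort 2 at 50 to 65 kg and 12 h, the raw ratio is 0.42 on Day 14 and 0.61 on Day 21. Normalising Day 28 by that day's tablet count gives 1.48 to 1.68 across the alternating bands at 12 h (true value 1.38), and 3.20 to 3.95 at 36.6 h (true value 2.83). Averaging a low and a high day and dividing by the mean count recovers 1.38 and 2.83.

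**The case for a change.** The strongest case for a change is that RA is the one quantity the PK criterion names, Section 3.2.2.1 points to no document that defines it, and the loading dose removes the conventional definition. At a 36.6 h half-life the same kinetics in Cohort 1 could be reported as 0.71 or 2.83. The first lies below every Table 3 AUC ratio and the second above every one. Section 3.2.2.2 carries the criteria over to individual subjects. In Cohort 1 the loading-to-daily tablet ratio runs from 3 (6/2) to 5 (5/1), so raw values could differ 5/3 = 1.67-fold between subjects with identical kinetics. A definition would cost one sentence.

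The textual point stands: the basis is not stated in what can be read. The harm does not follow. It needs a raw ratio, which nothing in the documents proposes, computed by a pharmacokineticist who ignores a dose change printed in Table 2. The contrast of 0.71 with 2.83 also needs the longest half-life in the quoted range. Evidence on proportionality is less thin than the 30 to 120 mg range suggests. Section 1.4 also calls the increase generally proportional without giving a range. The dog entry in Table 3 reports proportional exposure below the no-effect level, whose human equivalent of 278 µg/kg/day exceeds every nominal dose here.

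Nor does the protocol say that RA will be set against Table 3. Section 3.2 compares absolute Cmax and AUC with the animal values. The tablet calculation also shows that a quick one-line definition could mislead: normalising to that day's tablets would bias the ratio in six of the eight weight bands of Cohorts 2 and 3.

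**Conclusion.** No change to the plan is needed. The visible protocol leaves RA undefined, and the loading dose means that the definition needs some thought. But this is detail assigned to the PK Analysis Plan and the SRC charter, neither of which was available here. The PK sampling times and some parameter rows are also blacked out. Absence from the visible text does not show absence from the plan.

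The nominal factors at issue, 4, 2.67 and 2, are known in advance and removed by routine dose normalisation. What remains is the proportionality assumption, worth roughly 0.76- to 1.32-fold if b lies between 0.8 and 1.2, and the alternating tablet counts, which averaging over a low and a high day handles. Neither drives a decision mechanically. RA has no cut-off, the criterion is the SRC's judgement of clinical risk, and under Section 3.2.1 the committee reviews plasma PK and safety data to at least Day 14, with earlier cohorts' available data to Day 28 from the Cohort 2 review onwards.

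The ratios are illustrations under one-compartment, proportional kinetics and the half-lives quoted in Section 1.4, and do not predict what the trial will show. The conclusion would change only if the PK Analysis Plan or the charter specified an unadjusted ratio to Day 1, and nothing in the documents suggests that.
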